### 8.2.1. Overall Summary of Adverse Events

The following will be summarized:

- Number and percentage of patients with at least one SAE
- Number and percentage of patients with at least one related SAE
- Number and percentage of patients with at least one severe, related SAE
- Number and percentage of patients with at least one NSRAEs
- Number and percentage of patients with SAE leading to death

- Number of SAEs
- Number of related SAEs
- Number of severe related SAEs
- Number of NSRAEs
- Number of SAE/NSRAE leading to death

### 8.2.2. Summary of SAEs by System Organ Class, Preferred Term, Severity and Relationship

SAEs will be tabulated (n and %) within each severity category (mild, moderate, severe) and overall categories by system organ class and preferred term. In addition, the number of SAEs will be presented by relationship. Related SAEs are defined as those events coded as 'possible', 'probable' or 'very likely'. Non related SAEs are defined as those events coded as not related or doubtful. Counts will be given for both system organ class and preferred term. Each patient experiencing an SAE will be identified within preferred term and shown under the maximum severity relating to the particular preferred term. For overall severity categories, relationship of the AE will take priority over severity *ie* for the same patient a mild related headache will be counted over an unrelated severe headache.

<Protocol: Janssen OZ1-HV1-101/102/202>

<INC code: 1003733>

<SAP Version: 3.0>

---

For both system organ class and preferred term, counting will be done by patient and not by event. A patient will only be counted once within each system organ class and preferred term. The maximum severity for an event will be taken for each patient.

### **8.2.3. Summary of SAEs and Non-Serious Related Adverse Events by System Organ Class, Preferred Term, Outcome and Relationship**

SAEs and NSRAEs will be tabulated (n and %) within each outcome category (recovered/resolved, recovering/resolving, not recovered/not resolved, recovered with sequelae, fatal, unknown) by system organ class, preferred term. In addition, the number of SAEs and NSRAEs will be presented by relationship. Related SAEs are defined as those events coded as possible, probable or very likely. Not related SAEs are defined as those events coded as not related or doubtful. Counts will be given for both system organ class and preferred term. Each patient experiencing a related SAE will be identified within preferred term and shown under the outcome relating to the particular preferred term.

For both system organ class and preferred term, counting will be done by patient and not by event. A patient will only be counted once within each system organ class and preferred term.

### **8.2.4. Summary of Time Adjusted Related SAEs by System Organ Class and Preferred Term**

The number of related SAEs will be presented by system organ class and preferred term. In addition, event rate per year will be calculated using the formula below:

$$\text{Event rate per year} = \text{Number of related SAEs} / \text{Patient years in long term follow-up}$$

Where patient years in long term follow-up is calculated individually for each patient using the last available date of a safety assessment – (date of infusion + 2 yrs) and summed over all patients.

Each value from the above derivation will be totaled over each body system and preferred term to give a rate at which a particular related SAE may be experienced by a patient in a given year *ie* a patient rate per year of 1 for a particular preferred term is equal to a patient experiencing a related SAE once a year for the particular preferred term.

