1.2 Rationale for Study[†]

Food and Drug Administration (FDA)/Center for Biologics Evaluation and Research (CBER) recommends a 15-year time-period for follow-up observations. However, CBER also recognizes that assessment of risk is a continuous process, and the nature and duration of follow up observations may be revised accordingly.⁴ This follow up protocol is to assess the long-term safety of OZ1/LNL6 gene transfer product in patients who were enrolled in the OTH/OZ1-INT-1 study. Based on the integrated safety analysis of observations up to 10 years in this LTFU study, up to 15 years with the same OZ1/LNL6 gene transfer product in 2 Phase 1 LTFU studies (OZ1-HV1-101 and OZ1-HV1-102), and published reports of adverse events observed with gene therapeutic products using the same type of retroviral vector,^{2,3,5,6,7,8,10,11,12} the sponsor has determined that the risk to OZ1/LNL6 gene transfer product to recipients beyond 10 years post-infusion is minimal. Accordingly, this long term follow up study will conclude by 30 November 2017. This completion date represents a minimum of 10 years follow up following the receipt of OZ1/LNL6-modified CD34+ cells.

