10.2 Procedures

NON-SERIOUS ADVERSE EVENTS

Non-serious adverse events must be recorded using medical terminology in the source document and in the case report form if they have a possible, probable or very likely suspect association to the study drug.

SERIOUS ADVERSE EVENTS

All adverse events meeting the definition of serious, regardless of severity or presumed relationship, must be recorded using medical terminology in the source document and in the case report form. Only SAEs that are “possibly”, “probably” or “very likely” related to the study drug must be reported using the Sponsor Serious Adverse Event Form within 24 hours of knowledge of the event. Exceptions to this include:

- Death, regardless of the cause, is considered a reportable SAE;
- Malignancy (except Basal Cell or Squamous Cell Carcinomas), regardless of causality, is considered a reportable SAE.

Whenever possible, diagnoses should be given when signs and symptoms are due to a common etiology (e.g. cough, runny nose, sneezing, sore throat, and head congestion should be reported as “upper respiratory infection”). Investigators must record in the CRF their opinion concerning the relationship of the SAE to study therapy. All measures required for serious adverse event management must be recorded in the source document.

OZ1: Clinical Protocol OZ1-HV1-202 Amendment 4; 07 June 2017

Subjects (or their designees, if appropriate) must be provided with a “study card” indicating the name of the investigational product, the study number, the investigator’s name, and a 24-hour emergency contact number.

All reportable SAEs occurring during the study period must be reported to the appropriate sponsor contact person by investigational staff within 24 hours of their knowledge of the event. If the SAE is a death or a life threatening event the Investigator must notify the Sponsor immediately by both telephone and FAX.

Information regarding serious adverse events will be transmitted to the sponsor using the Sponsor Serious Adverse Event Form, which must be signed by a member of the investigational staff. The initial report of a serious adverse event may be made by facsimile (fax) or telephone. It is preferable that serious adverse events be reported via fax. Subsequent to a telephone report of a serious adverse event, a Serious Adverse Event Form must be completed by the investigational staff and transmitted to the sponsor within 24 hours.

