### 13. INDEX OF TABLES

Table Number	Table Description
14.1.1	Patient Disposition Including Reason for Discontinuation Summary Statistics: All Patients
14.1.2	Analysis Populations Summary Statistics: All Patients
14.1.3	Demographic Details Age, Gender and Race Summary Statistics: PP Population
14.1.4	Significant Medical History Time Since HIV-1 Infection Summary Statistics: PP Population
14.1.5	Treatment Details Summary Statistics: PP Population
14.1.5a	Treatment Details (Study 202 only) Summary Statistics: PP Population
14.1.6	Compliance Visit Attendance Summary Statistics: PP Population
14.2.1.1	OZ1 and LNL6 DNA PCR Marking Parameters (PBMC) Over Time: Actual Values Summary Statistics: PP Population
14.2.1.1a	OZ1 and LNL6 DNA PCR Marking Parameters (PBMC) Over Time: Actual Values (Study 202 only) Summary Statistics: PP Population
14.2.1.2	OZ1 and LNL6 DNA PCR Relationship of Marking Parameters (PBMC) with Calculated Dose, Age, Time on Study, Gender and Race Statistical Analysis: PP Population
14.2.1.2a	OZ1 and LNL6 DNA PCR Relationship of Marking Parameters (PBMC) with Calculated Dose, Age, Time on Study, Gender and Race (Study 202 only) Statistical Analysis: PP Population
14.3.1	Overall Summary of Adverse Events Summary Statistics: Safety Population
14.3.2	Serious Adverse Events By System Organ Class, Preferred Term, Severity and Relationship including Patient ID Summary Statistics: Safety Population
14.3.3	Serious and Non Serious Related Adverse Events By System Organ Class, Preferred Term, Outcome and Relationship including Patient ID Summary Statistics: Safety Population
14.3.4	Time Adjusted Serious Adverse Events By System Organ Class and Preferred Term Summary Statistics: Safety Population
14.3.5	Serious and Non-Serious Related Adverse Events Relationship Between Time on Study and Related Serious and Non Serious Adverse Events Summary Statistics: Safety Population

<Protocol: Janssen OZ1-HV1-101/102/202>

<INC code: 1003733>

<SAP Version: 3.0>

14.3.6	Patient Death By System Organ Class and Preferred Term, Including Patient ID Summary Statistics: Safety Population
14.4.1	Clinical History Experienced new or exacerbated pre-existing haematological disorders (including clinically significant laboratory abnormalities)? Summary Statistics: PP Population
14.4.2	Clinical History Had any new malignancies (including skin cancers)? Summary Statistics: PP Population

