SYSTEM ORGAN CLASS A												
PREFERRED TERM 1												
PREFERRED TERM 2												
ETC												

Note: Data summarized in this table are presented in data listing X.X.X.X  
 NR = Not related (those events with a relationship of not related or doubtful)  
 Rel = Drug-related adverse events (those events with a relationship of possible, probable or very likely)

DDMMYYYY HH:MM

*Prgm note: This table will continue for Fatal and Unknown categories and for OZ1-HV1-102, OZ1-HV1-202 and Overall*

<Protocol: Janssen OZ1-HV1-101/102/202>

<INC code: 1003733>

<SAP Version: 3.0>

Janssen - OZ1-HV1-101/102/202

TABLE 14.3.4

Page 1 of x

Time Adjusted Serious Adverse Events  
By System Organ Class, Preferred Term  
Summary Statistics: Safety Population

System Organ Class Preferred Term	OZ1-HV1-101	OZ1-HV1-102	OZ1-HV1-202	Overall
SYSTEM ORGAN CLASS 1				
Number of events				
Event rate per year				
PREFERRED TERM 1				
Number of events				
Event rate per year				
PREFERRED TERM 2				
Number of events				
Event rate per year				
SYSTEM ORGAN CLASS 2				
Number of events				
Event rate per year				
PREFERRED TERM 1				
Number of events				
Event rate per year				
ETC				

Note: Data summarized in this table are presented in data listing X.X.X.X  
Event rate per year = Number of related SAEs / Patient years in long term follow-up

*DDMMYYYY HH:MM*

<Protocol: Janssen OZ1-HV1-101/102/202>

<INC code: 1003733>

<SAP Version: 3.0>

Janssen - OZ1-HVI-101/102/202

TABLE 14.3.5

Page 1 of x

Serious and Non-Serious Related Adverse Events  
Relationship Between Time on Study and Related Serious and Non Serious Adverse Events  
Summary Statistics: Safety Population

Visit		Statistic	OZ1-HV1-102 / OZ1-HV1-202 (N = XX)	Overall (N = XX)
2.5 years post infusion	SAE	N (1) Rho (2) p-value		
	NSRAE	N (1) Rho (2) p-value		
3 years post infusion	SAE	N (1) Rho (2) p-value		
	NSRAE	N (1) Rho (2) p-value		
3.5 years post infusion	SAE	N (1) Rho (2) p-value		
	NSRAE	N (1) Rho (2) p-value		
Etc...	Etc...	Etc...		

Note: Data summarized in this table are presented in data listing x.x  
 (1) N = number of patients experiencing at least one event  
 (2) Rho = Spearman's Rank Correlation co-efficient

DDMMYYYY HH:MM

<Protocol: Janssen OZ1-HV1-101/102/202>

<INC code: 1003733>

<SAP Version: 3.0>

Janssen - OZ1-HV1-101/102/202

TABLE 14.3.6

Page 1 of x

Patient Death  
By System Organ Class, Preferred Term including Patient ID  
Summary Statistics: Safety Population

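### The plan's only rate over person-time counts investigator-judged related SAEs without an interval, so malignancies coded unrelated or doubtful enter no exposure-adjusted rate

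*SAP*

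**What the plan says.** SAP 8.2.4 plans one time-adjusted output, Table 14.3.4. Its numerator is restricted by causality: "The number of related SAEs will be presented by system organ class and preferred term". The footnote of the Table 14.3.4 shell repeats this: "Event rate per year = Number of related SAEs / Patient years in long term follow-up". The title in SAP section 13 drops the restriction: "Time Adjusted Serious Adverse Events By System Organ Class and Preferred Term".

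Events coded possible, probable or very likely count as related. SAP 8.2.2 puts the rest outside: "Non related SAEs are defined as those events coded as not related or doubtful". The judgement is the investigator's (Protocol 10.2): "Investigators must record in the CRF their opinion concerning the relationship of the SAE to study therapy". Under SAP 8.2 a missing relationship is set to very likely, so it counts as related.

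Protocol 10.2 also says: "Malignancy (except Basal Cell or Squamous Cell Carcinomas), regardless of causality, is considered a reportable SAE". Death is reportable whatever its cause. Insertional oncogenesis is objective 1b in both documents.

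Table 14.3.4 is assigned to the Safety population, which SAP 4.1 defines without any condition on treatment. SAP 4.2 limits the Per-Protocol (PP) population to patients who received OZ1, LNL6 or both. Placebo patients leave study 202 only once the parent trial is unblinded (Protocol 5.2 and 8).

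**The concern.** The main delayed hazard of an integrating retroviral vector is malignancy, and the protocol asks for malignancies to be reported whatever their presumed cause. The one analysis that relates events to years at risk then puts the causality filter back.

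The filter matters because an alternative explanation is always at hand. Protocol 10.1 makes doubtful the category for an event that a concomitant disease explains better, and every patient has HIV. Protocol 10.1 illustrates its stronger categories with dechallenge and rechallenge, which a single infusion does not allow. As background text since removed, Protocol Appendix 3 records a Kaposi's sarcoma in the Phase I CD34+ study that was attributed to AIDS rather than to the product. That attribution may well be right, and the event may predate follow-up, but an event coded that way falls outside the numerator.

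Once the placebo patients leave, no control rate is available to test the attributions. A rate of zero with no interval, or a table with no neoplasm row, says nothing about how large a rate the cohort could have missed.

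**Working it through.** The documents give no expected rate, precision target or person-time, and SAP 3.2 says no sample size was calculated. There is therefore no plan figure to reproduce. The check has three parts.

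**1. Is this the only rate over person-time?**

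- SAP 8.2.1 to 8.2.3 and 8.2.6 (Tables 14.3.1 to 14.3.3 and 14.3.6): counts and percentages of patients or events.
- SAP 8.2.5 (Table 14.3.5): a Spearman correlation.
- SAP 8.5 (Tables 14.4.1 to 14.4.6): percentages by visit. The shell has columns for clinic visit, telephone and overall, and none by study.
- SAP 8.2.4 (Table 14.3.4): events divided by patient-years.

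Only the last uses person-time. No confidence interval appears in SAP 8.2.4, in the table shell or elsewhere in the SAP.

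**2. What precision is left unstated? (study 202 only, assumed person-time)**

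The exact Poisson 95% limits for x events in PY patient-years are

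- lower = chi2(0.025; 2x) / (2 PY), taken as 0 when x = 0
- upper = chi2(0.975; 2x + 2) / (2 PY)

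At x = 0 the upper limit is 7.378 / 2 = 3.689 expected events. At x = 1 it is 11.143 / 2 = 5.572.

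| Assumed PY | Upper limit, 0 events (per 100 PY) | Upper limit, 1 event (per 100 PY) |
|---|---|---|
| 200 | 3.689 / 200 = 1.84 | 5.572 / 200 = 2.79 |
| 300 | 3.689 / 300 = 1.23 | 5.572 / 300 = 1.86 |

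This range can be tied to the documents. Protocol 1.1 gives 74 planned patients with about half on OZ1, so about 37. Protocol 1.2 gives at least 10 years after infusion, and SAP 8.2.4 starts the clock at 2 years, so a completer contributes at least 8. If all 37 entered and contributed 8 years each, PY = 37 × 8 = 296, and then:

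- 0 events: 0 (0 to 1.25) per 100 PY
- 1 event: 0.34 (0.01 to 1.88)
- 3 events: 1.01 (0.21 to 2.96)

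So if three malignancies occurred and all were coded not related or doubtful, they would add nothing to Table 14.3.4, against an all-cause rate of 1.01 per 100 PY. For zero events, the upper limit runs from 2.49 at 148 PY (37 × 4 years) to 1.00 at 370 PY (37 × 10 years).

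**3. What does placebo time do to the study 202 denominator?**

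The number of placebo patients who entered, and their time in follow-up, are not given. If 37 each contributed half a counted year, PY rises from 296 to 314.5, and any rate for treated patients is multiplied by 296 / 314.5 = 0.941. With one year each it is 296 / 333 = 0.889. Two events in treated patients would then show as 0.60 rather than 0.68 per 100 PY.

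**The case against.** The strongest reply is that nothing is hidden. Table 14.3.2 gives every SAE by preferred term, split by relationship and with patient identifiers. Table 14.3.3 does the same by outcome, and Table 14.3.6 gives deaths whatever the relationship. Table 14.4.2 tabulates new malignancies by visit, and Listing 16.2.8.2 lists every SAE. This stands. A reader might infer that malignancies judged unrelated vanish from the report; they do not. They are missing only from the rate.

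Related is also a broad category. It includes possible, and a missing relationship goes to very likely, so only events actively coded not related or doubtful drop out. The oncogenesis objective is also served by integration-site testing and retesting, oncogene mapping and tumour tissue sampling. Both points stand, and they limit the consequence without supplying a rate.

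A reader might also infer that this table underpins the decision to end follow-up, since Protocol 1.2 states that the risk "beyond 10 years post-infusion is minimal". The documents do not support that. The statement concerns risk after year 10 and cites integrated data from three studies plus published reports. It dates from June 2017, before the final analysis expected in 2018. The 2016 interim analysis fell under this SAP, but nothing shows that the statement relied on this rate.

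Nor does Protocol 10.2 say why malignancy is reportable regardless of causality. Reading it as distrust of the investigator's judgement is inference.

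Finally, the plan is descriptive, and an all-cause rate would have no comparator either. That is true, and it is a reason to show the interval rather than a reason to omit it.

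**Conclusion.** The concern holds in a limited form. The plan's only exposure-adjusted safety rate is filtered by investigator causality, carries no interval and is computed in a population that includes placebo time. Malignancies coded not related or doubtful are counted and listed but enter no rate, although insertional oncogenesis is an objective and no comparator continues.

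The size is illustrative and applies to study 202 only. With 200 to 300 patient-years assumed, zero events leaves rates up to 1.84 to 1.23 per 100 patient-years open, and one event up to 2.79 to 1.86. The Overall column has more person-time and would be tighter. The placebo dilution depends on numbers the documents do not give. The mismatch between title and footnote is a labelling fault, since the footnote states the restriction.

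This is a weakness in how a descriptive analysis reports precision. It is not an error in a test, and it does not show that any malignancy was missed.

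**What to change.** In SAP 8.2.4 and Table 14.3.4:

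- Keep the related-SAE rows.
- Add all-cause rates per 100 patient-years for all SAEs, malignancy and death.
- Define malignancy as in Protocol 10.2, without basal and squamous cell carcinoma, and say so in a footnote. SAP 8.5 includes skin cancers, so Table 14.4.2 can differ.
- Give exact Poisson 95% confidence intervals, and print zero-event rows with their upper limit.
- Take both the events and the patient-years from PP (treated) patients only, with the existing 8.2.4 person-time formula. Putting treated-only events over Safety-population years would understate the rate.
- Make the title agree with the footnote, and label each row as related or all-cause.

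The cost is a few rows in an existing table. SAEs are already recorded in the case report form whatever their relationship, and the dates are already used for the denominator. The downside is that the safety result is shown as less precise.

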1. INTRODUCTION

1.1 Background[†]

OZ1 is a Moloney Murine Leukemia Virus based retroviral vector (LNL6) containing a gene that encodes an anti-HIV-1 ribozyme directed against the human immunodeficiency virus type 1 (HIV-1) regulatory gene *tat*.^{13,14,15} A Phase I study demonstrated that the introduction of OZ1 into CD34+ cells *ex vivo* is technically feasible and safe.¹ The international, multi-center, Phase II, randomized, double-blind trial, OTH/OZ1-INT-1, was initiated to investigate the safety and efficacy of OZ1-transduced autologous CD34+ cells in patients with HIV-1 infection.⁹ One patient was enrolled in a Phase II protocol comparing the retroviral vector alone (LNL6) and OZ1. In a protocol amendment, OTH/OZ1-INT-1 became a placebo-controlled trial. Of the 74 patients to be enrolled in the placebo controlled protocol, approximately half received a placebo and half OZ1. The primary efficacy end point is the difference in viral load between the two groups at weeks 47 and 48 post-infusion. Patients continue in the OTH/OZ1-INT-1 treatment interruption follow-on phase until week 100 post-infusion as long as the viral load remains below 100,000 copies/ml, the CD4+ cell count is greater than 150 cells/mm³ and there are no other reasons to recommence antiretroviral therapy. At the end of the OTH/OZ1-INT-1 study (week 100 post-infusion), patients are invited to enter this long term follow-up (LTFU) protocol.

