10.1 Adverse Event Definitions and Classifications[†]

Adverse Event

An adverse event is any untoward medical occurrence in a clinical study subject administered a pharmaceutical product. An adverse event does not necessarily have a causal relationship with the treatment. An adverse event can therefore be any unfavorable and unintended sign (including an abnormal finding), symptom, or disease temporally associated with the use of a medicinal (investigational) product, whether or not related to the medicinal (investigational) product. (Definition per International Conference on Harmonisation [ICH]). This includes any occurrence that is new in onset or aggravated in severity or frequency from the baseline condition, or abnormal results of diagnostic procedures, including laboratory test abnormalities.

Note: The sponsor collects adverse events starting with the signing of the informed consent until completion of the subject's last study-related procedure.

Serious Adverse Event

A serious adverse event (SAE) as defined by ICH is any untoward medical occurrence that at any dose meets any of the following conditions:

- results in death;
- is life-threatening (the subject was at risk of death at the time of the event. It does not refer to an event that hypothetically might have caused death if it were more severe);
- requires inpatient hospitalisation or prolongation of existing hospitalisation;
- results in persistent or significant disability/incapacity;
- is a congenital anomaly/birth defect.

Medical and scientific judgment should be exercised in deciding whether expedited reporting is also appropriate in situations other than those listed above; for example, important medical events may not be immediately life-threatening or result in death or hospitalisation but may jeopardize the subject or may require intervention to prevent one of the outcomes listed in the definition above. Any adverse event is considered a serious adverse event if it is associated with clinical signs or symptoms judged by the investigator to have a significant clinical impact.

Any event requiring hospitalization (or prolongation of hospitalization) that occurs during the course of a subject's participation in a clinical study must be reported as a serious adverse event, except hospitalizations for:

- social reasons in the absence of an adverse event;
- surgery or procedure planned before entry into the study (must be documented in the source documentation and CRF)

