### **3. STUDY DESIGN**

#### **3.1. OVERVIEW OF STUDY DESIGN**

The OZ1-HV1-101, OZ1-HV1-102 and OZ1-HV1-202 studies form the long term follow-up for OZ1. OZ1 comprises a Moloney Murine Leukemia Virus based retroviral vector (LNL6) containing a gene that encodes an anti-human immunodeficiency virus (HIV) ribozyme. It is a recommendation of the United States Food and Drug Administration (FDA) that all individuals receiving retroviral gene transfer products are followed for life.

Patients who participated in the Phase I study “A Marker Study of Therapeutically Transduced CD4+ Peripheral Blood Lymphocytes in HIV discordant twins” were asked to continue long term monitoring under the OZ1-HV1-101 protocol. Patients who participated in the Phase I study “A Phase I Trial of Autologous CD34+ Hematopoietic Progenitor Cells Transduced with an Anti-HIV Ribozyme” were to continued long term monitoring under the OZ1-HV1-102 protocol. Patients who participated in the Phase II study “A randomized Phase II, double blind, controlled trial to evaluate the safety and efficacy of autologous CD34+ hematopoietic progenitor cells transduced with placebo or an anti-HIV ribozyme (OZ1) in patients with HIV-1 infection” continue long term monitoring under the OZ1-HV1-202 protocol. Following completion and unblinding of the Phase II study, patients who were identified as having been enrolled in the placebo arm were subsequently discontinued from the long term follow-up study 202.

All patients in each protocol will be reviewed at 6 month intervals (+/- 6 weeks) until year 5 post infusion. Thereafter, all patients will be reviewed annually (+/- 12 weeks) on the anniversary of their infusion. Given the recommendation to follow patients for life, patients who withdraw from the study or have been lost to follow-up but return for assessments at a later time may be re-instated in their study. Additional unscheduled visits may be made if any clinical or biological findings require further investigation. A schedule detailing the timing of the follow-up visits and the procedures carried out at each visit is presented in Table 1.

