Various data and samples have been collected under previous protocol versions. For data consistency across all the long term follow-up protocols only data corresponding to the schedule presented in Table 1 collected on one standardized Case Report Form (CRF) will be included in the data analysis. Additionally, the CRF will collect ‘Initial Study Information’ which will comprise of demography, significant medical history, treatment details from the respective original studies, and PBMC analysis and complete blood count (CBC)/differential and platelets results obtained 2 years post infusion or the nearest timepoint before starting the respective long term follow-up if 2 years post infusion data is not available.

<Protocol: Janssen OZ1-HV1-101/102/202>

<INC code: 1003733>

<SAP Version: 3.0>

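### The SAE rate's patient-years (SAP 8.2.4) ignore LTFU entry date and re-instatement gaps, so related SAEs and follow-up time need not cover the same period.

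*SAP*

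**What the plan says.** The shell for Table 14.3.4 gives the rate as "Event rate per year = Number of related SAEs / Patient years in long term follow-up". SAP 8.2.4 then defines the denominator: "Where patient years in long term follow-up is calculated individually for each patient using the last available date of a safety assessment", from which a fixed start is subtracted ("date of infusion + 2 yrs) and summed over all patients"). Neither place mentions an entry or consent date, or any interruption of follow-up.

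Four other statements bear on this:

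- **When events are collected.** Protocol 10.1, Note: "The sponsor collects adverse events starting with the signing of the informed consent until completion of the subject's last study-related procedure".
- **When patients enter study 202.** Protocol 1.1: "At the end of the OTH/OZ1-INT-1 study (week 100 post-infusion), patients are invited to enter this long term follow-up (LTFU) protocol". No latest entry date is given. SAP 3.1 accepts that the start varies, since baseline may be "the nearest timepoint before starting the respective long term follow-up if 2 years post infusion data is not available".
- **Gaps.** SAP 3.1: "patients who withdraw from the study or have been lost to follow-up but return for assessments at a later time may be re-instated". Protocol 7.1 and 8 allow re-entry until 30 November 2017, with no limit on the length of the gap.
- **Gap data.** SAP 6.2 tabulates patients who were discontinued and re-instated, and SAP Section 15 plans a listing of re-instatement details (16.2.1.2). The denominator uses neither.

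**The concern.** An event rate per patient-year is interpretable only if an event could have entered the numerator during every year counted in the denominator. The SAP definition does not ensure this at two points.

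1. **Entry.** A patient who consents after year 2 is credited with time before adverse event collection began.
2. **Gaps.** A patient who leaves and returns is credited with the whole absence, whether or not SAEs in that interval were later ascertained. Such a gap is credited only if the patient comes back, so the patient must have survived it. No fatal event can arise from that credited time, however good the recall on return.

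This is the only exposure-adjusted SAE rate in the SAP, and the first objective of the study is long-term safety. Where either mechanism operates without recovery of events, the product looks safer than the observed data show.

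**Working it through.** The documents state no event rate, patient-year total or number of re-instated patients, so there is no planned figure to reproduce. The SAP definition can be applied directly.

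**Formulas.** Let T be years from infusion to the last safety assessment, E the entry time in years, g the gap length, and r the share of gap SAEs recovered on return.

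- Credited time (SAP 8.2.4) = T − 2
- Observed time = T − E − g
- With a constant true rate and entry at or after year 2, SAP rate / true rate = (observed time + r × g) / (T − 2)

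**Inputs from the documents.** The start is infusion + 2 years (SAP 8.2.4). Entry to 202 is invited at week 100 (Protocol 1.1). Follow-up is at least 10 years (Protocol 1.2). E, g, r and the share of patients with gaps are not given, so the values below are assumptions.

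**One patient with a gap.** Lost at year 4, re-instated at year 8, last seen at year 11, observed from year 2:

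- Credited: 11 − 2 = 9 years
- Observed: (4 − 2) + (11 − 8) = 5 years
- r = 0: 5/9 = 0.56, so that patient's rate is 44% too low
- r = 0.5: (5 + 0.5 × 4)/9 = 0.78
- r = 1: 9/9 = 1, no bias

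**One such patient in ten**, the other nine observed for 9 years each: credited 9 × 9 + 9 = 90; observed 9 × 9 + 5 = 86; 90/86 = 1.047. Total time is overstated by about 5%.

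**Late entry.** Entry at year 2.5, last seen at year 10: credited 8, observed 7.5, ratio 0.94. This is 6% low for that patient. It would be a cohort figure only if every patient entered that late.

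**Early entry.** Week 100 is 700/365.25 = 1.916 years, so 2 − 1.916 = 0.084 years of observed time is left out. SAP 8.2.4 sets no onset limit on the numerator, so an SAE in that interval would still count. Over 8 years the ratio is 8.084/8 = 1.01, about 1% high. For a patient last seen at year 2.5 it is 0.584/0.5 = 1.17.

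**Cohort range.** Assume 37 patients (half of the 74 in Protocol 1.1; the number entering LTFU is not given), each followed to year 10, with no gap SAEs recovered. Credited time is 37 × 8 = 296 years.

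| Patients with a gap | Gap length | Observed years | SAP rate / observed-time rate |
|---|---|---|---|
| 10% | 1 year | 296 − 3.7 = 292.3 | 0.99 |
| 20% | 2 years | 296 − 14.8 = 281.2 | 0.95 |
| 30% | 5 years | 296 − 55.5 = 240.5 | 0.81 |

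**The case against.** A reader might infer that the SAP definition always lowers the rate. The documents do not support that, for two reasons.

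- A patient who enters 202 at week 100 has a short observed period left out, which pushes the rate up slightly.
- Gap time is not necessarily unobserved. The Appendix 2 telephone questionnaire asks about the period since the last visit or interview and whether events were serious. Protocol 7.1 provides for a nominated secondary contact, and SAP 8.5 records new malignancies and other disorders at each follow-up visit. If all SAEs in a gap are recovered, counting the gap is correct.

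Both points stand, but they limit the concern rather than remove it. The questionnaire is for patients who cannot be reviewed in clinic, and its health-care and hospitalization columns look back only 12 months, although its main questions cover the whole interval. No rule requires complete ascertainment of a gap before its time is counted.

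A reader might also infer that late consent did occur. It is permitted, but no passage shows it. The consent rule quoted is that of the 202 protocol, whereas the rate also covers 101 and 102, whose current protocols are not among the documents.

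The consequence is limited too. The analysis is mainly descriptive (Protocol 9), and SAP 8.2.4 attaches no test or threshold to this rate. SAE counts, patient percentages and listings do not depend on the denominator. With no related SAEs, the rate is zero under either definition.

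**Conclusion.** The point holds in a conditional form. SAP 8.2.4 lets the numerator and denominator cover different time, and the related-SAE rate is biased low to the extent that patients entered after year 2 or SAEs in gaps were not recovered on return. If everyone entered by year 2 and nobody had a gap, there is no downward bias, and entry at week 100 leaves a rate about 1% too high over 8 years.

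The actual size cannot be found from the documents. With one patient in ten having a four-year gap, total time is overstated by about 5%. Over the wider assumed ranges the SAP rate is 0.81 to 0.99 of the observed-time rate. Both figures assume that no gap SAEs are recovered. The 44% figure describes a single constructed patient and should not be read as a cohort effect.

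This is a minor but worthwhile correction to one descriptive safety table. It changes nothing in the conduct of the study.

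**What to change.** Redefine patient-years in SAP 8.2.4 and in the Table 14.3.4 footnote:

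1. Start each patient's time at LTFU entry: the consent date or, if that is not in the database, the first LTFU visit.
2. End it at the last safety assessment, as now.
3. Subtract every interval from discontinuation to re-instatement.
4. Count only related SAEs with onset in the time that remains.
5. As a sensitivity line, show the rate with gap time and the SAEs reported for the gap both included.

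Step 4 is essential. If gaps were subtracted while recovered gap SAEs stayed in the numerator, the rate would be overstated. For the patient above with full recovery, it would be 9/5 = 1.8 times the true rate.

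The cost is a few lines of SAP text and a small extra derivation. The discontinuation and re-instatement listings should supply the gap dates. The consent date is not among the initial study information named in SAP 3.1, so its availability must be checked, for 101 and 102 as well as 202.
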